8.1 Screening

Screening

The screening period will be a maximum of 4 days, and is used to check the participant's eligibility after obtaining informed consent and prior to the randomization on Day 1. The assessments required at screening are summarized in [Table 8-1](#). If all eligibility criteria are confirmed screening and randomization may occur on the same day.

8.1.1 Information to be collected on screening failures

Participants who consented and are subsequently found to be ineligible prior to randomization will be considered a screen failure. The reason for screen failure should be recorded on the appropriate Case Report Form. The demographic information, informed consent, and Inclusion/Exclusion pages must also be completed for screen failure participants. No other data will be entered into the clinical database for participants who are screen failures, unless the participant experienced a serious adverse event during the screening phase (see SAE section for reporting details). If the participant fails to be randomized, the IRT must be notified within 2 days of the screen fail that the participant was not randomized.

Participants who are randomized and fail to start treatment, e.g. participants randomized in error, will be considered an early terminator. The reason for early termination should be recorded on the appropriate Case Report Form.

8.2 Participant demographics/other baseline characteristics

All baseline assessments must be performed prior to first study treatment administration. These may be in the screening period (e.g. demographics) or at the randomization visit, depending on the assessment.

8.2.1 SARS-COV-2 testing

Respiratory tract specimen (e.g. nasopharyngeal swab, mid-nasal swab) will be taken for SARS-COV-2 PCR or rapid test and analyzed locally whether negative (or below LLOQ) or not to determine eligibility. If results of a previously performed test within 4 days prior to planned randomization date are available this does not need to be repeated for screening.

8.2.2 Demographic information

Demographic data to be collected at screening on all participants include: year of birth or age, gender, race, ethnicity and child-bearing potential (for females only).

Any relevant medical history including date of onset of COVID-19 disease symptoms, date of diagnosis of COVID-19 disease protocol solicited medical history, and/or current medical conditions before obtaining informed consent will be recorded in the Medical History CRF. Significant findings that are observed after the participant has provided informed consent and that meet the definition of an AE must also be recorded in the AE CRF. Whenever possible, diagnoses and not symptoms will be recorded.

Investigators will have the discretion to record abnormal test findings on the medical history CRF whenever in their judgment, the test abnormality occurred prior to the informed consent signature.

8.2.3 Prior and concomitant medications

Relevant prior and concomitant medications will be captured at the screening visit, and updated at the baseline visit. Any changes to the ongoing medications or any new concomitant medications will be recorded in CRF on an ongoing basis throughout study participation.

[REDACTED]

8.2.5 Other baseline characteristics

Baseline characteristic data to be collected for all participants listed below:

- ECG, vital signs, height and body weight
- [REDACTED]
- date and matrix (nasopharyngeal, oropharyngeal, other) of SARS-COV-2 test
- physical examination (to be recorded in source documents only)
- chest imaging (date and method of assessment – x-ray or CT scan, normal or abnormal – any clinically relevant findings to be reported in medical history)
- Any other testing required for inclusion/exclusion criteria

8.3 Efficacy

8.3.1 COVID-19 Participant status

The following details on the participants' status will be collected in the at Baseline and hospital discharge at a minimum, in addition any change in status must be reported in the CRF:

- Hospitalization (including dates of admission and discharge* or ready for discharge)
- ICU stay (including dates of admission** and discharge***)
- Pre-morbid supplemental oxygen requirements and its volume if yes (start and stop dates, volume: L)
- Mechanical ventilation requirements (start and stop dates)
- Participant survival status (i.e. death)

[REDACTED]

* If a participant is unable to be discharged due to administrative reasons, then the date that the participant, in the opinion of the investigator, is ready to be discharged (i.e. ready for discharge as evidenced by normal body temperature and respiratory rate, and stable oxygen saturation on ambient air or $\leq 2L$ supplemental oxygen) should be reported in the hospitalization status for date of discharge.

** In the case that a participant cannot be admitted to the ICU, even if the participant's condition is severe enough in the opinion of the investigator (e.g. due to administrative reasons under the current circumstances), this is also considered under admission and date of ICU admission should be reported

***If a participant is unable to be discharged from ICU due to administrative reasons, then the date that the participant, in the opinion of the investigator, is ready to be discharged should be reported in the ICU status for date of discharge.

[REDACTED]

8.3.2 SARS-COV-2 testing

At each SARS-COV-2 testing time point post screening detailed in [Table 8-1](#) a respiratory tract specimen (nasopharyngeal swab) will be taken for SARS-COV-2 PCR testing. This sample will be analyzed at a specialist virology lab to determine whether negative (or below LLOQ) or not. An additional sample may be collected and sent to the central lab for future quantitative analysis. Additional details on sample collection and shipping are provided in the laboratory manual.

In order to maintain consistency, every effort should be made to use the same sample site (i.e. nostril) for all post baseline assessments in individual participants.

8.3.3 Appropriateness of efficacy assessments

Efficacy assessments are assessments of standard supportive care required to treat COVID-19 disease. Events that are clearly consistent with the expected pattern of progression of the underlying disease should not be recorded as adverse events (with the exception of death due to COVID-19 disease progression). These data will be captured as efficacy assessment data only.

8.4 Safety and tolerability

Safety assessments are specified below with the assessment schedule detailing when each assessment is to be performed.

For details on AE collection and reporting, refer to AE section.

8.4.1 Physical examination

Information for all physical examinations must be included in the source documentation at the study site. Significant findings that are present prior to informed consent being obtained must be included in the Relevant Medical History/Current Medical Conditions CRF. Significant findings made after informed consent is given which meet the definition of an Adverse Event must be recorded on the Adverse Event screen of the participants CRF.

8.4.2 Vital signs and body measurements

Systolic and diastolic blood pressure (mmHg), pulse rate (bpm), will be recorded. Peripheral oxygen saturation (SpO₂, %) should be also measured at the same time as vital signs, height in centimeters (cm) will be reported at screening visit only.

Weight in pounds (lbs) or kilograms (kg), and body temperature (including method of collection) in Centigrade (°C) or Fahrenheit (°F) will be recorded.

8.4.3 Laboratory evaluations

Laboratory test will be conducted as per [Table 8-1](#) by local lab. Details on the parameters are listed below in [Table 8-2](#).

Clinically significant abnormal results for hematology, chemistry and urinalysis will be reported in the laboratory results CRF and as an AE, otherwise all these results will be kept in the source documents and will not need to be recorded in CRF. [REDACTED]

Table 8-2 Laboratory parameters (local lab)

Test Category	Test Name
Hematology	Hematocrit, hemoglobin, platelets, red blood cells, white blood cells (WBC), absolute differential WBC count (basophils, eosinophils, lymphocytes, monocytes, neutrophils, bands, other)
Chemistry	Alkaline phosphatase, alanine transaminase (ALT), aspartate aminotransferase (AST), calcium, magnesium, potassium, creatinine, direct bilirubin, total bilirubin, blood urea nitrogen (BUN), glucose, troponin (I or C as available), CPK
Urinalysis (dipstick)	Specific gravity, pH, protein, glucose and blood
Pregnancy Test	Serum / Urine pregnancy test
[REDACTED]	[REDACTED]

8.4.4 Electrocardiogram (ECG)

ECGs (preferably 12-lead) must be recorded after 10 minutes rest in the supine position to ensure a stable baseline. The preferred sequence of cardiovascular data collection during study

visits is ECG collection first, followed by vital signs. The Fridericia QT correction formula (QTcF) should be used for clinical decisions.

On Day 1 an ECG must be performed pre-dose and at 4 hours post dose.

Single ECGs (preferably 12-lead) will be collected using the sites own ECG machines and key parameters and the original trace available within the source data. A copy of the local tracing will be sent to a central ECG reader for additional safety evaluations. Any identifier details must be redacted e.g. subject initials, date of birth prior to sending to the central reader.

If participants are monitored by continuous telemetry, an assessment should be reported in the CRF for one time point on days when ECG monitoring is required and a copy of ECG tracing for this time point sent to the central ECG reader. In case of clinically significant findings the unscheduled visit can be used to report findings and an adverse event form completed if applicable.

For any ECGs with potential participant safety concerns, two additional ECGs (preferably 12-lead) must be performed to confirm the safety finding. A local monitoring or review process should be in place for clinically significant ECG findings throughout the study. Clinically significant abnormalities must be recorded on the CRF as either medical history/current medical conditions or adverse events as appropriate.

Given the known QT prolonging effect and treatment regimen of both HCQ and AZI, measure ECG until Day 4, then if required by the investigator from Day 6.

Please also refer to the cardiac safety monitoring [Section 10.2.1](#) for additional details.

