4.2.3 Rationale for dose regimen

The proposed hydroxychloroquine (HCQ) regimen is 600 mg loading dose followed by 200 mg three times daily for the first 10 days of the study. The total treatment duration of hydroxychloroquine will be a maximum of 10 days. The approach includes a loading dose on Day 1 to reach the target concentration in the lung tissue within the first 5 hours. The proposed regimen is expected to enable optimal inhibition of both viral and inflammatory pathways by HCQ. Three times a daily regimen is selected to mitigate C_{max} related to cardiac safety risk.

Recently published literature describes the effect of HCQ on the replication of SARS-CoV-2 and similar coronaviruses, *in vitro*. Full dose response curves of the antiviral activity of HCQ in an *in vitro* assay using Vero E6 kidney epithelial cells infected with SARS-CoV-2 have been published (Yao et al 2020). Depending on the time point (24 or 48 hours post infection) the EC₅₀ values range from 0.72 – 6.25 μ M and the EC₉₀ values from 1.5 – 15 μ M. Furthermore, HCQ EC₅₀ values of 8 μ M have been reported in similar *in vitro* assays for other human-tropic coronaviruses (Dyall et al 2014). Based on the totality of *in vitro* data, we anticipate a significant effect of HCQ on SARS-CoV-2 viral load in patients at an HCQ target concentrations of greater than 15 μ M (5040 ng/mL) of free base in lung tissue.

The HCQ PK model was constructed based on published clinical data (Tett et al 1988 and Tett et al 1989). The combined clinical data was best described by a 3-compartment model with

absorption into and linear elimination from the central compartment, and distribution into peripheral compartments. The human PK parameters from the 3-compartment model are summarized in [Table 4-1](#). The simulations took into consideration that an oral dosage form of 200 mg hydroxychloroquine sulfate contains 155 mg hydroxychloroquine. The large volume of distribution indicates that HCQ is highly bound to tissues. To simulate the concentration of HCQ in the lung we assume direct and rapid partitioning from the central compartment with a partition coefficient of $K_p = 50.6$ ([Wei et al 1995](#)).

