The simulated concentration time curves for HCQ in the lung and blood for either 600 mg o.d. HCQ sulfate (light gray, regimen), or a loading dose of 600 mg followed by 200mg t.i.d. (dark red) are presented in [Figure 4-1](#). Additionally, co-administration of azithromycin is not expected to have an effect on HCQ concentrations ([Yeates et al 1996](#) and [Mattila et al 1994](#)).

The dosing regimen of 600 mg loading dose followed by 200 mg t.i.d. hydroxychloroquine sulfate enables rapid attainment and maintenance of the target lung concentration of 15 μM . [Table 4-2](#) summarizes the C_{max} , C_{min} and AUC values for HCQ in blood.

Figure 4-1 Predicted concentrations of hydroxychloroquine in the lung and blood compartments

[figure not shown]

Figure 4-1: A regimen consisting of a 600 mg HCQ sulfate loading dose on Day 1 followed by 200 mg t.i.d. (red) is compared against a 600mg o.d. regimen (grey). While the y-axis represents concentrations of HCQ (free base), doses are expressed as HCQ sulfate tablets. The horizontal line denotes a target threshold of 15 μ M (5040 ng/mL). a) Predicted PK profile for day 1 b) Predicted PK profile from day 1 to day 10 c) Predicted PK profile followed by a washout period to reach the threshold of EC90.

Table 4-1 Human PK parameters from 3-compartment model describing human total blood hydroxychloroquine

Parameter	Units	Estimate	95% Confidence Interval
V1	L	193.6	[161.1,228.7]
V2	L	3519.1	[3024.6,4150.2]
CL	L/h	5.67	[5.37,5.99]
Q12	L/h	2.42	[1.95,3.05]
ka	1/h	0.156	[0.125, 0.199]
F	dimensionless	0.79 (fixed)	
V3	L	2274.5	[2021.1,2546.1]
Q13	L/h	47.5	[40.9,54.9]

Table 4-2 Predicted human exposure for 600 mg loading dose and 200 mg t.i.d. maintenance dose of hydroxychloroquine sulfate

		Mean	95% Confidence Interval
Cmax (ng/mL)	Day 1, 0-8hr	511.8	[433.2, 600.3]
	Day 1	525.2	[460.9, 600.3]
	Day 10	1128.6	[1059.4, 1197.8]
Cmin (ng/mL)	Day 1	382.15	[342.4, 417.8]
	Day 10	1012.5	[944.4, 1087.3]
AUC (ng/mL*hr)	Day 1	10603	[9484, 11696]
	Day 10	25690	[24080, 27413]

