setting. Participants should also be closely monitored for signs and symptoms of hypoglycemia, particularly those who are diabetic and taking anti-diabetic medications. More relevant to the short term administration of HCQ and azithromycin is drug-induced QT interval prolongation and potential pro-arrhythmic effects. To that end, in addition to relevant cardiac exclusion criteria, participants will also need to follow cardiac safety monitoring, with clear guidance on when to discontinue study medications with regard to QTcF changes. In the setting of active COVID-19 disease in the study population, the benefits of short-term treatment in a hospital setting should, in principle outweigh the known potential risks.

Women of child-bearing potential and sexually active males must be informed that taking the study treatment may involve unknown risks to the fetus if pregnancy were to occur during the study, and agree that in order to participate in the study they must adhere to the contraception requirements outlined in the exclusion criteria. If there is any question that the participant will not reliably comply, they should not be entered or continue in the study.

5 Study Population

The study population will consist of approximately 444 male and female adult participants with moderate to severe COVID-19 disease receiving standard of care to be randomized into hydroxychloroquine, hydroxychloroquine plus azithromycin, or placebo in 1:1:1 ratio (148 participants / arm).

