6.1.3 Treatment duration

The total treatment duration of hydroxychloroquine is 10 days. The approach to include a loading dose on Day 1 is preferred in order to rapidly reach higher target tissue drug concentrations. The total treatment duration of azithromycin will be 5 days.

In case a participant is discharged prior to Day 10, they may complete study treatment as planned, at home, until Day 10 if QTcF \leq 480 ms at the time of discharge based on the local ECG data. Otherwise, treatment will be discontinued at the time of discharge.

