Inclusion / Exclusion criteria	X	X								
Demography	X									
Medical history/current medical conditions	X									
Chest imaging	X ³							X ³		
Randomization		X								
Drug dispensation and administration					X					
Pregnancy test (serum and urine dipstick)	X									
Physical Examination, vital signs and body measurements ²	X	X	X	X	X	X	X			X
SARS-COV-2 test	X ⁴	X			X		X			X
Electrocardiogram (ECG)	X	X ⁵	X	X	X ⁶		X ⁶			X
Laboratory assessments (hematology, chemistry, urinalysis, ██████████) ⁷	X			X			X	X ³		
Biomarker plasma and serum		X					X	X		
Prior and concomitant medications							X			
Adverse Events							X			
Study completion information							X			

X Assessment to be recorded in the clinical database or received electronically from a vendor, ¹ All assessments for unscheduled visits are optional, ²Height and weight collected at screening only, ³ If available record findings, ⁴ If results of a previously performed test within 4 days prior to planned randomization are available this does not need to be repeated for screening ⁵ pre-dose and 4 hours post dose, ⁶ If required in the opinion of the Investigator. ⁷Hematology: Hct, Hgb, PLT, RBC, WBC, differential WBC count; Chemistry: ALP, ALT, AST, Ca, Mg, K, creatinine, direct and total bilirubin, BUN, glucose, troponin (I or C), CPK, ██████████

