10.2 Additional Safety Monitoring

10.2.1 Cardiac safety monitoring

In case of QTcF > 500 msec and QTcF prolongation > 60 msec from baseline, please take the following steps:

- Temporarily interrupt study treatment
- Assess the quality of the ECG recording and the QT value and record two additional ECG tracings to confirm the values
- Determine the serum electrolyte levels (in particular hypokalemia, hypomagnesemia and/or hypocalcemia). If abnormal, correct abnormalities before resuming study treatment.
- Review concomitant medication use for other causes for QT prolongation (refer to qt drugs.org for known QT prolonging drugs) and for drugs with the potential to increase the risk of drug exposure of study drugs
- Check the dosing schedule and treatment compliance
- Increase cardiac monitoring as indicated, (consider continuous telemetry monitoring) until the QTcF returns to ≤ 480 msec
- If QTcF is ≤ 480 msec prior to the next dose, continue dosing with another ECG collected 4 hrs post dose
- If QTcF remains > 480 msec prior to the next dose discontinue study treatment for the participant permanently

In case of persistent QTcF > 500 msec and QTcF prolongation > 60 msec from baseline and/or documented new onset arrhythmia (e.g. Torsade de Pointes, Ventricular Tachycardia) or syncope - discontinue treatment for the participant and request evaluation by a cardiologist.

Please refer to [Appendix 1](#) for notable vital signs.

Local practices should be followed to ensure participant safety for Liver and Renal monitoring, in addition below are suggested guidelines for safety monitoring.

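### Day 4 is the last ECG required of every participant, although hydroxychloroquine dosing runs to Day 10 and the protocol's own model has blood levels still rising

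*Protocol*

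**What the plan says.** ECGs are required at screening, on Day 1 (before dosing and 4 hours after), on Day 2 and on Day 4. After that, section 8.4.4 says to "measure ECG until Day 4, then if required by the investigator from Day 6". In Table 8-1 the ECG cells for Day 6 and Day 10/early discharge carry footnote 6, "If required in the opinion of the Investigator", and there is no ECG cell for Day 8 or Day 15. SAP 2.8.4.1 repeats this schedule.

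HCQ is given for 10 days and azithromycin for 5 (section 6.1.3). On dose, section 4.2.3 says: "Three times a daily regimen is selected to mitigate C_{max} related to cardiac safety risk". Table 4-2, headed "Predicted human exposure for 600 mg loading dose and 200 mg t.i.d. maintenance dose of hydroxychloroquine sulfate", shows Cmax rising from 525.2 ng/mL on Day 1 to 1128.6 ng/mL on Day 10.

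Section 4.5 answers the arrhythmia risk with cardiac exclusions and monitoring, "with clear guidance on when to discontinue study medications with regard to QTcF changes". The operative rule is in section 10.2.1: "In case of QTcF > 500 msec and QTcF prolongation > 60 msec from baseline, please take the following steps". The first of those steps is to interrupt study drug.

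Some ECG requirements do reach past Day 4:
- Participants discharged early: "they may complete study treatment as planned, at home, until Day 10", provided QTcF is at most 480 ms at discharge (section 6.1.3).
- After any ECG that raises a safety concern, "two additional ECGs (preferably 12-lead) must be performed to confirm the safety finding" (section 8.4.4).
- Section 10.2.1 asks for repeat and post-dose ECGs once its QTcF trigger has been met.

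**The concern.** The QTcF stopping rule works only if QTcF is measured. Each requirement that survives Day 4 depends on either early discharge with home dosing or an ECG that has already raised concern. A participant who stays in hospital on study drug and had unremarkable ECGs to Day 4 meets neither condition.

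QTcF prolongation without symptoms gives the investigator no clinical prompt to order an ECG. It would therefore not set off the section 10.2.1 interruption. That section also stops drug for new arrhythmia or syncope, but those are the events the QTcF threshold is there to prevent.

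What is at stake is mainly patient safety. Late prolongation that is never recorded would also be absent from the any-time QTcF counts in SAP 2.8.4.1.1. Those analyses are descriptive and only 20 participants were randomized, so the effect on inference is small.

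**Working it through.** **Inputs.** All come from Protocol sections 4.2.3 and 6.1.2.
- Regimen: 600 mg HCQ sulfate at 0 h, then 200 mg every 8 h from 8 h to 232 h.
- Salt to base: 155/200 = 0.775, so 465 mg and 155 mg base. F = 0.79.
- Table 4-1: V1 193.6 L, V2 3519.1 L, V3 2274.5 L, CL 5.67 L/h, Q12 2.42 L/h, Q13 47.5 L/h, ka 0.156 per h.

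**Model.** Three compartments with first-order absorption. A is drug at the absorption site, raised by F × base dose at each dosing time.
- dA/dt = −ka·A
- V1·dC1/dt = ka·A − CL·C1 − Q12·(C1 − C2) − Q13·(C1 − C3)
- V2·dC2/dt = Q12·(C1 − C2)
- V3·dC3/dt = Q13·(C1 − C3)

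**Reproducing Table 4-2 first.**

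| Quantity | Model | Table 4-2 |
|---|---|---|
| Day 1 Cmax, 0–8 h (ng/mL) | 510.5 | 511.8 |
| Day 1 Cmax (ng/mL) | 520.1 | 525.2 |
| Day 1 AUC (ng/mL·h) | 10,644 | 10,603 |
| Day 10 Cmax (ng/mL) | 1126.7 | 1128.6 |
| Day 10 Cmin (ng/mL) | 991.7 | 1012.5 |
| Day 10 AUC (ng/mL·h) | 25,865 | 25,690 |

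Agreement is within about 2%, so the model can be read at days the protocol does not print.

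**Exposure by day.** Percentages are of the Day 10 peak, 1126.7 ng/mL. The daily minimum falls at the start of the day, before the first dose.

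| Day | Minimum | Peak | Minimum, % | Peak, % |
|---|---|---|---|---|
| 4 | 548.6 | 705.6 | 49 | 63 |
| 6 | 715.7 | 864.3 | 64 | 77 |
| 8 | 862.6 | 1003.8 | 77 | 89 |
| 10 | 991.7 | 1126.7 | 88 | 100 |

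For Day 4, 705.6/1126.7 = 0.626.

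**Sensitivity of the Day 4/Day 10 peak ratio.**
- All 128 combinations of the lower and upper 95% limits of the seven estimated parameters: 0.598 to 0.660.
- A 12 h gap after the loading dose: 0.637.
- Maintenance dosing from 24 h: 0.594.
- Three maintenance doses on Day 1: 0.642.

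**Dosing still to come.** There are 1 + 29 = 30 HCQ doses, or 600 + 29 × 200 = 6,400 mg. Doses from time t onward number (232 − t)/8 + 1.
- After Day 4 (from 96 h): 18 doses, 18 × 200 = 3,600 mg, and 3,600/6,400 = 56%.
- After Day 6 (from 144 h): 12 doses, which is four full days.
- From the start of Day 8 (168 h): 9 doses.
- From the start of Day 10 (216 h): 3 doses. The modelled peak is at about 235 h, after the last dose.

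**The case against.** The best defence is that the schedule is deliberate. Section 8.4.4 bases it on the QT effect and regimens of both drugs, and azithromycin runs Days 1 to 5, so the Day 4 ECG falls inside combined dosing. This stands for the combination arm: the documents give no azithromycin pharmacokinetics, so the time of greatest combined risk cannot be derived. It does not help the HCQ-only arm, where predicted exposure is highest on Day 10.

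A second objection is that exposure is not risk. This also stands. A reader might take 63% to mean that the Day 4 ECG captures 63% of the QT effect. The documents do not support that: they give no concentration–QTc relation, and the Cmax remark in section 4.2.3 justifies splitting the daily dose, not a claim about accumulation over ten days.

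Third, the plan has further safeguards:
- telemetry where used, unscheduled ECGs, and a local review process for significant ECG findings (section 8.4.4, Table 8-1);
- a ban on QT-prolonging drugs throughout the study (Table 6-2);
- Day 10 chemistry including potassium, magnesium and calcium (Tables 8-1 and 8-2);
- a possible pause after more than two cases of Torsade de Pointes or ventricular tachycardia with marked QTcF prolongation (section 9.1.4).

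So it would be wrong to infer that participants are unmonitored after Day 4. These provisions reduce the risk, but none obliges a site to record an ECG in an uneventful inpatient who is still dosing.

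Finally, an ECG on Day 10 comes too late to prevent much: it can stop three doses at most. This is correct and shapes the fix.

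**Conclusion.** The gap is real. Every ECG after Day 4 is discretionary for a participant dosing in hospital without an earlier ECG concern, while 18 of 30 HCQ doses remain and modelled blood HCQ has reached about 63% of its Day 10 peak (77% on Day 6, 89% on Day 8). The result rests on the Table 4-1 model and the stated regimen.

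It concerns HCQ exposure only. The size of any missed QTcF effect cannot be computed, and neither can the number of participants affected, because the documents do not say how many would still be dosing in hospital without a discretionary ECG.

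A reader might go further and conclude that the SAP's ECG summaries must be rebuilt. That does not follow. They are descriptive, SAP Table 2-3 already maps unplanned ECGs from Days 8 to 12 to the Day 10 row when the scheduled one is missing, and reporting detail does not close a gap in monitoring.

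The change should be made in any restart or reuse of this schedule. Enrolment here stopped at 20 randomized participants.

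**What to change.** In Table 8-1, remove footnote 6 from the Day 6 and Day 10/early discharge ECG cells. Amend section 8.4.4 to require an ECG at those visits for anyone still on study drug, and cross-reference the discharge ECG to section 6.1.3, which already needs a QTcF before home dosing.

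Day 6 matters most, because four days of dosing remain after it. The Day 10 ECG should be taken before that day's first dose. Alternatively, replace it with one at the existing Day 8 visit, which already takes vital signs: taken before the first dose, it leaves nine doses that could still be stopped. This option means adding a Day 8 ECG cell and keeping the early discharge ECG mandatory.

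The cost is up to two more single ECGs per participant (2 × 444 = 888 at the planned size), on the sites' own machines at visits already scheduled, with the tracings sent to the central reader. No change to the SAP analyses is needed.
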